In an exploratory endoscopy substudy, subjects with more severe disease at the Visit 2 ileocolonoscopy (a SES-CD  $\geq$ 7, if ileum and colon are involved or  $\geq$ 4 if only the ileum is involved) will undergo a second ileocolonoscopy at the end of treatment (Day 42) to evaluate changes in the mucosa.

Pharmacokinetic (PK) evaluations will be based on concentrations of V565 measured in serum and urine. Safety will be assessed through evaluations of adverse events (AEs), clinical laboratory results, vital signs, physical examinations, electrocardiograms (ECGs) and concomitant medications.

Planned number of subjects:	Approximately 126 randomised to receive study drug in a
3	2:1 active:placebo ratio (84:42)
	Approximately 114 to complete (76:38) based on an estimated dropout
	rate of 10% during treatment

Diagnosis and main criteria for inclusion:	This study will enrol adult subjects with active CD. The main criteria for inclusion are:
	
 
History of CD (confirmed by ileocolonoscopy) of at least three months duration prior to Visit 1
 
CDAI score of ≥220 to ≤450 during Screening
 
CRP ≥5 mg/L (or, if CRP is normal, FCP ≥250 µg/g) at Screening
 
Active CD of ileum and/or colon as determined by the baseline ileocolonoscopy
 
Female subjects must not be pregnant and male and female subjects must agree to use effective contraception throughout the study and for 90 days after the last dose of study drug.
 
Subject must have failed or experienced intolerance to at least one of the following: aminosalicylates, corticosteroids; immunosuppressants (e.g., azathioprine [AZA], 6-mercaptopurine [6-MP], or methotrexate [MTX]).
 

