### 6.1.3 Biomarkers of Inflammation

The collection of CRP and/or FCP will occur at the time points indicated in .

C-reactive protein is an acute-phase reactant produced in the liver and is an easily measured non-specific marker of inflammation. It is a widely used marker of inflammation in CD and elevations in CRP have been associated with endoscopic inflammation in CD [15, 16].

C-reactive protein will be analysed in blood samples. If CRP values are normal, FCP will be assessed in the faecal samples. FCP will be used as the eligibility test if CRP results are <5 mg/L. During the treatment and follow up phase of the study, FCP will only be evaluated in subjects whose screening CRP was <5 mg/L, and who qualified for the study based on their screening FCP value.

Calprotectin is abundant in the cytosol of activated neutrophils. The amount of FCP is directly proportional to neutrophil influx into the intestinal tract and is a reliable non-specific marker of intestinal inflammation [17, 18, 19]. While currently endoscopy with biopsy is considered the gold standard for evaluating the extent and location of inflammatory mucosal lesions, studies have shown that FCP may also be a useful marker of intestinal inflammation.

On Day 1, the faecal sample for FCP should be collected prior to administration of the first dose of study drug. The subject may also provide a sample from faeces passed one day prior to the scheduled visits. These samples will be collected in sterile containers (to be provided to the subjects) and refrigerated at home. At each sampling time point, approximately 2 g to 5 g of faeces will be collected.

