### **3.3.** CHANGES TO ANALYSIS FROM PROTOCOL

In the protocol section 8.2.1 it is mentioned that the baseline CRP and baseline FCP results will be included as covariates in the statistical model for logistic regression. CRP or FCP will be used to determine inflammation status at baseline. Some subjects may appear 'normal' on the basis of their CRP result however the FCP measurement reveals the presence of inflammation. As FCP will be measured for subjects only if CRP is <5 mg/L, FCP will be missing for many subjects. In addition, the CRP result for subjects who entered on the basis of inflammation measured by a FCP result => 250 ug/g will not be meaningful as a reflection of inflammation status. For these reasons neither FCP nor CRP will be incorporated into the primary model fit. However, if a subject is enrolled in the study based on the baseline result of FCP the definition of response will incorporate a 40% reduction in CRP. If a subject is enrolled in the study based on the baseline result of FCP the definition of response will incorporate a 40% reduction in CRP.

STATISTICAL ANALYSIS PLAN: PROTOCOL V56502 Page 12 of 40

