#### 15. **EFFICACY OUTCOMES**

#### 15.1. **PRIMARY EFFICACY**

#### 15.1.1. **PRIMARY EFFICACY VARIABLE & DERIVATIONS**

The primary efficacy variable is Responders at Day 42

A Responder is defined as subjects achieving both CDAI ≥70-point reduction from Baseline OR CDAI score <150, and a reduction of  $\geq$ 40% from the baseline value of CRP (where CRP at baseline => 5mg/dL) or FCP (where CRP at baseline <5mg/dL and FCP at baseline =>250 ug/g)

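### SAP 15.1.1 chooses the primary-endpoint biomarker at a CRP of 5 mg/dL (50 mg/L), ten times the 5 mg/L qualifying cut, and SAP 3.3 separately judges FCP-enrolled subjects on CRP

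*SAP*

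**What the plan says.** The protocol defines response by a CDAI criterion together with a reduction of at least 40% in CRP or FCP (Synopsis, 2.3, 8.2.1). It does not say which marker applies to which subject.

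On eligibility and measurement the protocol is consistent. The Synopsis requires "CRP ≥5 mg/L (or, if CRP is normal, FCP ≥250" µg/g. Section 6.1.3 states that "FCP will be used as the eligibility test if CRP results are <5 mg/L" and that, after screening, "FCP will only be evaluated in subjects whose screening CRP was <5 mg/L" and who qualified on FCP.

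Twice the visible SAP text says which marker counts for response.

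- **SAP 15.1.1** uses "CRP (where CRP at baseline => 5mg/dL" for one branch and "FCP (where CRP at baseline <5mg/dL and FCP at baseline =>250 ug/g" for the other.
- **SAP 3.3** explains why CRP and FCP were dropped as covariates. It notes "As FCP will be measured for subjects only if CRP is <5 mg/L, FCP will be missing for many subjects", and says that CRP in subjects who entered on FCP "will not be meaningful as a reflection of inflammation status". It then states, in two identical sentences, that for a subject enrolled "based on the baseline result of FCP the definition of response will incorporate a 40% reduction in CRP". It has no sentence for subjects enrolled on CRP.

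**The concern.** There are two independent faults in the rule that decides the biomarker half of the primary endpoint.

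1. **Unit.** The cut in 15.1.1 is in mg/dL, while eligibility and FCP testing use mg/L. The printed selector therefore does not match the data that will exist.
2. **Marker.** SAP 3.3 judges FCP-enrolled subjects on CRP, whereas 15.1.1 judges them on FCP. Correcting the unit does not remove this conflict, because the unit error does not change the marker for a subject whose CRP is below 5 mg/L.

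15.1.1 is the derivation section and so the natural source for programming. Followed literally, it leaves some CRP-qualified subjects without a marker. How they would then be counted cannot be read, because the imputation criteria announced in 15.1.2 are not visible. If 3.3 were followed instead, FCP-enrolled subjects could meet the biomarker half on a small movement in CRP, whatever happened to FCP. The CDAI half would still be required in either case.

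**Working it through.** **Inputs.** Selector cut: 5 mg/dL (SAP 15.1.1, both brackets). Qualifying cut: 5 mg/L (protocol Synopsis, 4.1, 4.2.1, inclusion criterion 6, 6.1.3, 6.1.5; SAP 3.3 and 5.2). FCP cut: 250 µg/g. Reduction required: 40%. The CRP and FCP values below are illustrations, not trial data.

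**Step 1: the unit.** 1 mg/dL = 10 mg/L, so 5 mg/dL = 50 mg/L. Ratio to the qualifying cut: 50 / 5 = 10.

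**Step 2: the printed selector.** The rule is CRP if baseline CRP is at or above the cut; otherwise FCP if baseline FCP is at least 250 µg/g; otherwise no marker.

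| Baseline CRP, mg/L (mg/dL) | FCP, µg/g | Cut as printed, 5 mg/dL | Cut at 5 mg/L |
|---|---|---|---|
| 3 (0.3) | 400 | FCP | FCP |
| 5 (0.5) | not measured | none | CRP |
| 20 (2.0) | not measured | none | CRP |
| 49 (4.9) | not measured | none | CRP |
| 50 (5.0) | not measured | CRP | CRP |

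The gap runs from 5 to below 50 mg/L. If a screening FCP of at least 250 µg/g happened to exist for such a subject, the printed rule would choose FCP. Protocol 6.1.3 would then not follow FCP on treatment.

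**Step 3: whether correcting the unit is enough.** The brackets select on values at baseline. SAP 6.2 takes the CRP and FCP baseline as the last non-missing value before Day 1, unscheduled values included, so it can be later than the value on which the subject qualified. With the unit corrected to mg/L:

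| Qualifying values at screening | Later baseline value | Selecting on baseline | Selecting on screening |
|---|---|---|---|
| CRP 6, no FCP | CRP 4 | none | CRP |
| CRP 4, FCP 300 | CRP 6 | CRP | FCP |
| CRP 4, FCP 300 | FCP 240 | none | FCP |

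The screening selector gives the marker on which the subject qualified in all three cases. It also matches protocol 6.1.3, which ties on-treatment FCP to screening CRP.

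**Step 4: what SAP 3.3 would require.** The CRP fall needed by an FCP-enrolled subject is 0.4 × baseline CRP:

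- baseline 4.0 mg/L: 0.4 × 4.0 = 1.6 mg/L;
- any baseline below 5 mg/L: less than 0.4 × 5 = 2.0 mg/L;
- a later baseline of 6 mg/L: 0.4 × 6 = 2.4 mg/L.

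FCP plays no part in this version of the rule.

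**The case against.** The strongest reply is that both faults are evident slips. Every other statement of the cut is in mg/L, and SAP 3.3, which lists the changes from the protocol, declares no new threshold. The duplicated sentence looks like a copying error, with one copy presumably meant for CRP-enrolled subjects. SAP 10 summarises baseline CRP and FCP by the marker on which subjects qualified, so the intent is recoverable, and a literal program would probably be caught. Part of 15.1.1 and the sample code in Appendix 3 are not visible and may hold the detailed algorithm. The re-measurement cases also depend on a further sample between qualification and Day 1, and the schedule table that would show one is not visible.

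Much of this is fair. The intent can be inferred, the unseen text supports no claim either way, and the frequency of the re-measurement cases is unknown.

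It does not remove the point. The protocol's bare choice of CRP or FCP cannot settle the matter. The visible definition of the composite secondary endpoint in SAP 15.2.1 is equally bare, and SAP 10 is not a response rule. That leaves two explicit statements, one with the wrong threshold and one naming the wrong marker, and no hidden text would make them agree. The re-measurement cases have support in the text: SAP 6.2 admits unscheduled values, protocol 6.1.3 accepts a faecal sample from the day before a visit, and protocol 6.2.3 has blood drawn at every visit.

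**Conclusion.** The concern holds on both counts, and the text must be corrected before unblinding. The threshold error is exactly tenfold. As printed, 15.1.1 assigns no marker to CRP-qualified subjects with baseline CRP from 5 to below 50 mg/L, provided FCP is measured only as protocol 6.1.3 and SAP 3.3 describe. SAP 3.3 contradicts 15.1.1 on the marker for FCP-enrolled subjects. Its small required falls in CRP arise only if 3.3 is followed in place of 15.1.1.

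The documents do not give the proportion of subjects affected, so neither a direction of bias nor a loss of power is claimed.

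**What to change.** In the SAP, before unblinding:

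1. **Section 15.1.1.** Reword the two brackets to select on the qualifying screening value in mg/L, for example: *CRP for subjects who qualified with screening CRP ≥5 mg/L; FCP for subjects with screening CRP <5 mg/L who qualified on FCP ≥250 µg/g; where a screening test was repeated, the re-test decides.* The last clause follows protocol 4.2.1. Keep the 40% reduction measured from the SAP 6.2 baseline of the selected marker.
2. **Section 3.3.** Replace the two identical sentences with: *enrolled on CRP, a reduction of at least 40% in CRP; enrolled on FCP, a reduction of at least 40% in FCP.*

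The cost is two reworded brackets and one replaced pair of sentences. No new data are needed, and the 40% criterion does not change.

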### 6.2.3 Clinical Laboratory Evaluations

Blood will be drawn and urine samples will be collected from each subject at each study visit. The clinical laboratory parameters used as screening tests, efficacy outcomes or for safety monitoring are presented in Table 2.

Clinical laboratory tests will be reviewed for results of potential clinical significance throughout the study (see Section 6.2.1 for definition of clinically significant laboratory results). If the Investigator determines a laboratory abnormality to be clinically significant, it is considered a laboratory AE. However, if possible, the underlying condition causing the laboratory abnormality, rather than the abnormality itself, should be reported as the AE. Clinically significant laboratory results will be followed to resolution or until the Investigator considers the abnormality chronic and/or the subject to be stable.

A central laboratory designated by the Sponsor will be used for all laboratory assessments during the trial. Urine pregnancy testing will be done by dipsticks (supplied by the central laboratory).

If an immediate result is required, a sample should be sent to both the local and central laboratory.

Haematology:	Serum Chemistry:	
White blood cell count (differential, percentages and	Sodium	
absolute count)	Potassium	
Haemoglobin	Blood urea nitrogen/Urea	
Haematocrit	Creatinine	
Red blood cell count	Glucose	
Mean corpuscular volume	Calcium	
Mean corpuscular haemoglobin	Phosphorus	
Mean corpuscular haemoglobin concentration	Total protein	
Red cell distribution width	Albumin	
Platelet count	Aspartate aminotransferase	
	Alanine aminotransferase	
Urinalysis:	Total bilirubin	
Colour	Alkaline phosphatase	
Clarity/Appearance		
Specific gravity	Additional Tests (Females of childbearing potential):	
pH	Serum pregnancy test (at Visit 1)	
Protein	Urine pregnancy at Day 1, Day 42 and Day 56	
Blood	If the urine pregnancy test gives equivocal results at	
Glucose	these visits, or is positive, a serum pregnancy test	
Ketones	will be performed to determine if the subject is	
Bilirubin	pregnant.	
Urobilinogen		
Nitrite	Biomarkers	
Leukocyte esterase	C-reactive protein	
Microscopy	Faecal calprotectin	
Additional Tests (Screening only):		
Activated partial thromboplastin time		
Hepatitis B surface antigen		
Hepatitis B surface antibody		
Hepatitis B core total antibody		
Hepatitis C antibody		
C. difficile toxin and presence of other enteric		
pathogens		
QuantiFERON-TB Gold Test		
×		

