# 8.2 Statistical Methods

The default summary statistics for continuous variables include number of contributing observations [n], mean, standard deviation (SD), median, minimum, and maximum.

For categorical variables, the number and percentage (the percentage of subjects in each category relative to the total number of subjects in the relevant analysis population or relative to the total number of subjects in the relevant analysis population, with assessments available [where appropriate]) in each category will be the default summary presentation.

Unless otherwise specified, "Baseline" is defined as the last observed value of the parameter of interest prior to the first intake of study medication (this includes unscheduled visits). For numerical variables, change from Baseline will be calculated as the difference between the value of interest and the corresponding baseline value.

Unless otherwise specified, all formal statistical tests will be two-sided at the 5% significance level. Point estimates of treatment differences will be accompanied with two-sided 95% confidence intervals (CIs) where applicable.

In the case of normality assumption violations, appropriate non-parametric methods will be used for analysis.

All data will be presented in by-subject listings.

The statistical analysis will be performed using SAS® Version 9.2 or higher.

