### 6.2. BASELINE

Unless otherwise specified, baseline is defined as the last non-missing measurement taken prior to first administration of study drug (including unscheduled assessments). In the case where the last non-missing measurement and the reference start date coincide, that measurement will be considered pre-baseline, but Adverse Events (AEs) and concomitant medications commencing on the reference start date will be considered post-baseline.

For the endpoints of CRP and FCP, the baseline score is the last non-missing measurement taken prior to Day 1 (including unscheduled assessments).

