### **10.** DEMOGRAPHIC AND OTHER BASELINE CHARACTERISTICS

Demographic data and other baseline characteristics will be presented for the ITT, SAF and PP populations.

No statistical testing is planned for demographic or other baseline characteristics.

Summaries for continuous and categorical variables (as described in section 6) will be presented for each treatment and Total.

Demographics and baseline characteristics will be presented in a listing by subject.

The following demographic and other baseline characteristics will be reported for this study

- Age (years) at screening as collected from eCRF
- Sex
- Race
- Ethnicity
- Body Weight (kg) at screening
- Height (cm) at screening as collected from eCRF
- BMI (kg/m^2) at screening as collected from eCRF
- Prior Anti-TNF Therapy
- Childbearing potential for female subjects
- Disease duration (months)
- Baseline CDAI score
- Baseline CRP for patients qualifying on CRP
- Baseline FCP for patients qualifying on FCP
- Baseline SES-CD score
- Prior CD medication use

STATISTICAL ANALYSIS PLAN: PROTOCOL V56502 Page 20 of 40

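### SAP 15.1.1 picks the response marker by re-testing the CRP and FCP cuts at baseline, while the protocol fixes the followed marker at screening, so an eligible subject can fit neither branch or be judged on the other marker

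*SAP*

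**What the plan says.** SAP 15.1.1 adds to the CDAI condition a fall of at least 40% in one inflammatory marker. The marker is chosen by a condition on baseline values. The fall is measured "from the baseline value of CRP (where CRP at baseline => 5mg/dL"), or else in "FCP (where CRP at baseline <5mg/dL and FCP at baseline =>250 ug/g"). The CRP cut is read here as 5 mg/L, the eligibility value; the printed mg/dL is a separate error.

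For CRP and FCP, SAP 6.2 says that "the baseline score is the last non-missing measurement taken prior to Day 1 (including unscheduled assessments"). Protocol 8.2 differs: baseline "is defined as the last observed value of the parameter of interest prior to the first intake of study medication", which would admit a pre-dose sample on Day 1.

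Protocol 6.1.3 settles which marker is followed by what happened at screening. In treatment and follow-up, "FCP will only be evaluated in subjects whose screening CRP was <5 mg/L" and who entered the study on their FCP result. The same section also has a general rule, "If CRP values are normal, FCP will be assessed in the faecal samples".

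Two other parts of the SAP follow the qualifying marker. Section 10 lists "Baseline CRP for patients qualifying on CRP" and the equivalent for FCP. Section 3.3 ties the response marker to the result on which the subject was enrolled, but its wording is garbled: it pairs FCP enrolment with a CRP reduction, and prints that sentence twice.

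**The concern.** The branch condition in SAP 15.1.1 and the sampling rule in Protocol 6.1.3 use two different pre-treatment values. They agree when each subject has one pre-treatment result per marker. They can disagree when a second result, taken after the qualifying one and before Day 1, lies on the other side of a cut. The subject is then either in no branch, or in the branch of a marker on which they did not qualify.

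This is the primary endpoint. With no written rule, whoever programs the endpoint must decide whether an unclassified subject is a non-responder, is missing and to be imputed, or is scored on the qualifying marker. If the gap is found after unblinding, that choice is post hoc. If the text is applied literally, some subjects who met the CDAI and marker criteria are scored as failures in both arms, which costs sensitivity.

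**Working it through.** **Step 1: what each crossing leads to.** Inputs: the two branch conditions in SAP 15.1.1, with cuts of 5 mg/L and 250 µg/g, and the FCP follow-up rule in Protocol 6.1.3.

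| Qualified on | Later pre-Day 1 value | Branch under SAP 15.1.1 | Consequence |
|---|---|---|---|
| CRP | CRP still ≥5 | CRP | as intended |
| CRP | CRP <5, no FCP run | neither | status undefined |
| CRP | CRP <5, FCP run and ≥250 | FCP | Protocol 6.1.3 provides no on-treatment FCP |
| FCP | CRP <5, FCP still ≥250 | FCP | as intended |
| FCP | CRP <5, FCP <250 | neither | status undefined, although FCP is being followed |
| FCP | CRP ≥5 | CRP | can respond, but not on the qualifying marker |

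If the marker is fixed by screening qualification, every eligible subject falls in exactly one branch.

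**Step 2: where a second value could come from.**
- *Visit 2 or an unscheduled sample.* Possible. Protocol 6.2.3 says "Blood will be drawn and urine samples will be collected from each subject at each study visit", and its laboratory table lists CRP and FCP, but it does not say that either is run at Visit 2. The Schedule of Events is not in the text available for review, so this is unconfirmed. SAP 6.2 admits unscheduled values.
- *Eligibility retest.* Not a route. Protocol 4.2.1 lets the retest replace the original value for eligibility, so the qualifying value and the baseline move together.
- *Day 1 pre-dose sample.* Not a route under SAP 6.2, which stops before Day 1. It becomes one only under the Protocol 8.2 baseline.

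**Step 3: size.** The plan gives no figure for this and no CRP distribution, so everything here is assumed. Let T be log true CRP, normal with mean log(m) and SD 0.9. The qualifying, later pre-Day 1 and Day 42 values are

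X1 = T + e1, X2 = T + e2, X3 = T + log(1 − d) + e3,

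with independent errors of SD s and true CRP reduction d. Every subject is given a second value.

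- Unclassified share of CRP qualifiers: P(X2 < log 5 | X1 ≥ log 5).
- Share of CRP-component responders lost: P(X2 < log 5 | X1 ≥ log 5 and X3 − X2 ≤ log 0.6).

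Results from 2 million draws per row; the loss range runs from d = 0 to d = 50%:

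| Median m (mg/L) | s | Unclassified | CRP-component responders lost |
|---|---|---|---|
| 8 | 0.3 | 9% | 1.6% to 5.4% |
| 8 | 0.45 | 13% | 3.1% to 7.2% |
| 8 | 0.6 | 17% | 4.6% to about 9% |
| 12 | 0.3 | 6% | 0.8% to 3.2% |
| 12 | 0.45 | 9% | 1.7% to 4.2% |
| 12 | 0.6 | 12% | 2.5% to 5.1% |
| 20 | 0.3 | 3% | 0.3% to 1.4% |
| 20 | 0.45 | 4% | 0.6% to 1.8% |
| 20 | 0.6 | 6% | 1.0% to 2.3% |

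The loss is smaller than the unclassified share because a subject whose baseline is already low must fall further still: from 4 mg/L, a 40% reduction means reaching 0.6 × 4 = 2.4 mg/L or less. Part of the low baseline is also measurement error that tends to reverse.

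If only a fraction g of subjects has a second value, the unclassified share is multiplied by g. At g = 0 it is zero. FCP was not modelled.

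**The case against.** The strongest reply is that the gap may never arise. Retests and, under SAP 6.2, Day 1 samples are closed routes, and a Visit 2 CRP or FCP cannot be confirmed. The intent is also recoverable. The cuts in SAP 15.1.1 are the eligibility cuts, SAP 10 speaks of the qualifying marker, and SAP 3.3 points the same way despite its wording, so baseline in 15.1.1 may simply mean the qualifying result. The visible section may also be incomplete: SAP 15.3.1.2 refers to a CDAI derivation there that does not appear in the available text. Finally, the rule is the same in both arms, so it does not inflate type I error.

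Most of this stands, and it limits the size and urgency of the point. It does not remove it. SAP 6.2 gives CRP and FCP their own baseline definition, that definition is not the qualifying value, and it admits unscheduled samples. Nothing visible says which marker applies when the two values disagree.

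A reader might go further and infer that anyone crossing a cut is a certain non-responder because FCP was never run. The documents do not support that. An FCP qualifier whose CRP rises gets the CRP branch and can respond. One whose FCP drops below 250 µg/g falls out because the cut is re-tested, not because FCP is unavailable. And SAP 15.1.2 imputes missing responder status by criteria that are not shown, so undefined is the accurate word; non-response is only the literal reading.

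**Conclusion.** The inconsistency is real: SAP 15.1.1 selects the marker on a value that need not be the one that decided eligibility and FCP follow-up. Its effect depends on a later pre-Day 1 result that is not a retest, so the number affected cannot be derived from the documents and may be zero.

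On the assumed CRP model, 3% to 17% of CRP qualifiers would be unclassified and about 0.3% to 9% of CRP-component responders lost; at median 12 mg/L and within-subject SD 0.45 the loss is about 2% to 4%. These figures cover the CRP condition alone, not the composite with CDAI. It is tempting to multiply both response rates, and hence the treatment difference, by one minus the unclassified share. That overstates the damage, because it assumes that unclassified subjects would have responded at the average rate.

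In the same model 21% to 54% of subjects with a first CRP below 5 mg/L would have a second at or above it. That describes a switch of marker, not a loss, and it does not condition on FCP of at least 250 µg/g.

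This should be fixed, because it leaves a primary-endpoint derivation open to a later choice. The documents do not show it to be a large source of bias or lost power.

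**What to change.** In SAP 15.1.1, set each subject's marker once: CRP for those who qualified on CRP at screening, FCP for those who qualified on FCP, using the final eligibility value after any retest. Do not apply the 5 mg/L or 250 µg/g cut again to the baseline value. Calculate the 40% reduction from the SAP-defined baseline of that marker. Use the same marker for the secondary endpoint that requires a 50% reduction.

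At the same time, correct SAP 3.3 so that each enrolment marker is paired with its own reduction, state whether a Day 1 pre-dose sample can be the baseline so that SAP 6.2 and Protocol 8.2 agree, and correct the CRP unit in the same sentence of 15.1.1.

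The cost is a few sentences in the SAP before unblinding. The qualifying marker comes from the eligibility data already collected, and no new data are needed.
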